3.0 Specific Aims

Specific aim 1: to evaluate whether mifepristone will produce rapid symptom reduction after seven days of active treatment, as measured by Borderline Personality Disorder Severity Index (BPDSI) total score. Further, to evaluate whether seven days of mifepristone treatment will result in a durable improvement in symptoms persisting after active treatment discontinuation, as measured by Borderline Personality

Disorder Severity Index (BPDSI) total score.

Specific aim 2: to evaluate safety and tolerability of mifepristone

Specific aim 3: to assess cortisol levels as a potential biomarker of HPA-axis engagement.

Exploratory Aims: to assess clinical and demographic moderators of response to mifepristone, including childhood abuse characteristics (e.g., type of abuse, age of onset, duration) and comorbid psychiatric illnesses.

Outcome Measures: The primary outcome measures will be the Borderline Personality Disorder Severity Index (BPDSI) total score. With this measure, we will be able to investigate specifically the effect of mifepristone on BPD's entire psychopathologic spectrum. For inclusion, all subjects must demonstrate a minimum severity of a total score ≥ 3 on the CGI-S. Secondary outcomes will include the BPDSI symptom domain subscales, the Brief Psychiatric Rating Scale (BPRS), the self-report Borderline Checklist, the Symptom Checklist-90-Revised (SCL-90-R), improvement in metacognitive capacity, and the Clinical Global Impressions-Severity (CGI-S) and Clinical Global Impressions-Improvement (CGI-I) measures. Clinical assessments will be performed by trained raters, who will be blind to subjects' treatment condition.

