4.0 Study Design

This is a single site safety and proof of concept study conducted at the Indiana University Psychotic Disorders Program. Twenty four subjects with borderline personality disorder will be randomized 1:1 to double-blind treatment with oral mifepristone or matched placebo for duration of seven days, with a follow up period.

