10.0 Laboratory Assessments

Laboratory assessments (blood and urine) will be collected at time points specified in Study Procedures Table (Attachment 1) and analyzed by a local laboratory with the exception of the urine dipstick

assessments which will be collected and analyzed onsite.

A total of ~16ml of blood will be collected for screening assessments (Visit 1), ~28ml will be collected at baseline (Visit 2), ~17ml will be collected at Day 7 (Visit 4), ~12ml will be collected at Day 14 (Visit 5), and ~22ml will be collected at Day 28 (Visit 6).

Laboratory assessments to be completed:

Complete Blood Count with differential (CBC w/diff)
Comprehensive Metabolic Panel (CMP)
Pregnancy testing: serum and urine
Cortisol (must be drawn +/- 30 minutes of initial Visit 2 draw time)
Pharmacokinetics
Optional Biobank blood sample

Pharmacokinetics

Six ml of blood will be collected for trough mifepristone plasma concentration analysis (sent for analysis to MicroConstants in San Diego, CA).

Optional Biobank Blood Sample

An additional 10ml of whole blood will be collected (at Visit 2 and Visit 6) and sent to the Indiana Clinical and Translational Sciences Institute (CTSI) from all subjects who sign a separate consent and will be stored for later analyses, such as genetic examination. Subjects may refuse to participate in the repository without consequence to their participation in the main study. Non-identifying demographic information will be submitted to the CTSI at the time of sample submission. Subjects will be able to request sample destruction from the CTSI repository by formal request to the main study site.

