16.0 Statistical Considerations

Continuous variables will be summarized by treatment groups using descriptive statistics including mean, standard deviation, and range. Categorical variables will be summarized using frequency counts and percentages. Baseline clinical and demographic data will be compared between the two treatment groups to assess the effectiveness of the randomization. Dichotomous and ordinal variables will be examined using chi-square tests and continuous measures with Student's t-tests. Appropriate exact and non-parametric methods will be used as needed. The primary goal of this study will be to estimate the effect size for the treatment on the BPDSI total score. This will be done at each time point, as we are also interested in how the effect is sustained after active drug treatment is discontinued. We also will graph the trajectory of each subject over time. Supportive analyses will be based on the linear mixed effects model with a random subject effect for BPDSI with time, treatment and time by treatment interaction as covariates. The model parameters will be estimated using SAS MIXED procedure and the p-values for the comparisons of the differential treatment effects and 95% confidence interval for the treatment effect will be reported. The time by treatment interaction will be assessed to examine whether the active drug effect was changing over time. Secondary outcomes and serum cortisol levels will be examined similarly. Graphs, Pearson or Spearman correlations, and linear mixed models will be used to examine the relationship between serum cortisol levels and outcome measures. Due to the small sample size, covariates (type of abuse, age of abuse onset, abuse duration, diagnosis of MDD, diagnosis of PTSD) will be examined graphically. Safety analyses of this study will include summarized counts and rates per treatment group of the incidence of the adverse events. Incidences of selected adverse events from the two treatment arms will be compared using the Fisher's exact test on an exploratory basis.

Sample Size Justification: This is a pilot study designed to estimate effect sizes for a future randomized trial. It is recommended that a minimum of 12 subjects per group be used for this purpose based on estimating the precision of the meant treatment effect and variance (13).

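### If Day 0 is an outcome row in the supportive mixed model, the omnibus time-by-treatment test cannot show whether the drug effect held or faded after treatment stopped

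*Combined protocol and SAP*

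**What the plan says.** Specific aim 1 (section 3.0) asks first about rapid symptom reduction after seven days of treatment, and then whether "seven days of mifepristone treatment will result in a durable improvement in symptoms persisting after active treatment discontinuation". Section 4.0 gives the design as treatment "for duration of seven days, with a follow up period".

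Section 16.0 makes estimation of the effect size on BPDSI total score the primary goal. It does this at every time point because "we are also interested in how the effect is sustained after active drug treatment is discontinued". Supportive analyses use a "linear mixed effects model with a random subject effect for BPDSI with time, treatment and time by treatment interaction as covariates". The interaction is then given a job: "The time by treatment interaction will be assessed to examine whether the active drug effect was changing over time". Secondary outcomes and serum cortisol are to be handled in the same way.

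The Study Procedures Table (Attachment 1) schedules the 7-day BPDSI at Visits 2, 4, 5 and 6, which are Days 0, 7, 14 and 28. Section 10.0 identifies Visit 2 as baseline. The plan does not say whether the Day 0 score is an outcome row, a covariate or neither. It does not say whether time is categorical or linear, and it names no contrast between Day 7 and the later visits.

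**The concern.** The useful question about change is whether the drug-placebo difference seen at Day 7, the end of treatment, is still there at Days 14 and 28. An interaction test that includes Day 0 asks something else: whether the difference is the same at all four visits. Randomisation makes the expected difference zero on Day 0. A drug that works and keeps working therefore violates the null hypothesis, as does a drug that works and wears off.

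A significant interaction could then be reported as a changing drug effect when the effect had been stable since Day 7. The same would apply to other outcomes on the same four-visit schedule (BPRS, BPD Checklist, SCL-90-R, cortisol). The study exists to inform a later trial, so a mistaken message about persistence could be carried into that design.

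**Working it through.** **The plan's own figure.** 2 x 12 = 24 agrees with the stated sample size. The 12 per group is a rule of thumb with no alpha, power, effect or SD behind it. No power is stated for the interaction, so there is none to reproduce.

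**Inputs from the documents.** 12 per arm; BPDSI on Days 0, 7, 14 and 28; random subject effect; fixed time, treatment and interaction.

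**Assumptions, because the documents give no values.** Two-sided alpha 0.05 (suggested by the 95% CI); SD 1 at each visit; Day 7 effect d of 0.5 to 1.0 SD; within-subject correlation rho of 0.3 to 0.7; complete data; categorical time.

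**Formula.** Let e_t be the drug-placebo difference at visit t in SD units, and S = sum of (e_t - mean e)^2. In the balanced random-intercept model the interaction F test has noncentrality lambda = (n/2) x S / (1 - rho). Its degrees of freedom are 3 and 66 with four visits, and 2 and 44 with Days 7, 14 and 28 only.

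**Day 0 included.**
- Sustained (0, d, d, d): mean 0.75d, so S = (0.75^2 + 3 x 0.25^2)d^2 = 0.75d^2.
- Lost by Day 14 (0, d, 0, 0): mean 0.25d, so S = (0.75^2 + 3 x 0.25^2)d^2 = 0.75d^2.

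The two values of S are identical, so the rejection probability is the same for any d, rho or n. At d = 0.8 and rho = 0.5, lambda = 6 x 0.48 / 0.5 = 5.76.

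Rejection probabilities at d = 0.8, rho = 0.5:

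| Pattern after Day 7 | S, with Day 0 | With Day 0 | S, Days 7-28 | Days 7-28 only |
|---|---|---|---|---|
| Sustained | 0.75d^2 | 47.5% | 0 | 5.0% |
| Lost by Day 14 | 0.75d^2 | 47.5% | 0.667d^2 | 48.5% |
| Gradual loss (half at Day 14, none at Day 28) | 0.6875d^2 | 43.9% | 0.5d^2 | 37.7% |
| Lost only by Day 28 | 1.0d^2 | 60.6% | 0.667d^2 | 48.5% |

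**Other values.** The shared rate for sustained and lost by Day 14, with Day 0 included, is 20.2% at d = 0.5 and 68.3% at d = 1.0 (rho = 0.5). At d = 0.8 it is 34.8% for rho = 0.3 and 71.4% for rho = 0.7.

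**Sensitivity to the model.**
- Random-intercept F test applied to serially correlated data (simulation, d = 0.8): sustained versus lost by Day 14 is 51.5% versus 55.5% under AR(1), and 60.0% versus 65.5% under exponential decay. The equality becomes approximate.
- Unstructured covariance with such data (d = 1.0): 69% versus 90%, or 86% versus 99%. The gap widens, but a sustained effect is still rejected often.
- Linear time in days (d = 0.8, rho = 0.5): 36.6% for sustained against 10.7% for lost by Day 14. The test then points the wrong way.

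**What a post-baseline analysis can deliver.** Power of the Days 7-28 interaction for gradual complete loss is 16.9% to 25.8% at 0.5 SD and 37.7% to 58.2% at 0.8 SD, for rho of 0.5 to 0.7. For the Day 28 minus Day 7 contrast, SE = sqrt(2(1 - rho) x 2/12), which is 0.408 SD at rho = 0.5 and 0.316 SD at rho = 0.7. With t(44) = 2.015 the 95% CI half-widths are 0.82 and 0.64 SD.

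**The case against.** The strongest reply is that the premise is not in the text. Section 16.0 never says that Day 0 is an outcome row. It treats baseline comparison separately, and it speaks of the active drug effect, which does not exist on Day 0. If only Days 7, 14 and 28 are modelled, the test rejects 5% of the time for a sustained effect and works as intended. This stands as a limit on certainty. But with no baseline covariate listed, that reading would leave the Day 0 score out of the model altogether, so including it as a row is the more natural reading. Either way the text has to settle it.

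A reader might infer that the plan cannot answer the durability half of aim 1. The documents do not support that. Section 16.0 ties the interest in persistence to the effect size at each time point, which is the primary analysis. The Day 14 and Day 28 estimates show directly whether benefit remains, individual trajectories are graphed, and the mixed model is only supportive. What those estimates lack is an interval for the change between visits, and that is the question the interaction is meant to address.

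A reader might also infer that a non-significant interaction would be declared durability. No such rule appears. It is a risk in reporting, not something the plan states.

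Finally, the similarity of rejection rates depends on the loss pattern and time coding: loss only by Day 28 gives 60.6%, and linear time separates the rates. That is correct, but neither case makes a significant result interpretable as loss of effect.

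**Conclusion.** The point holds, conditional on Day 0 being an outcome row. Under categorical time and the stated random subject effect, the omnibus interaction cannot distinguish an effect sustained to Day 28 from one lost by Day 14. That equality is algebraic and does not depend on the assumed effect, correlation or sample size. The common rate does depend on them: 47.5% at 0.8 SD and correlation 0.5, and 20.2% to 71.4% over the cases shown for 0.5 to 1.0 SD at correlation 0.5 and for 0.8 SD at correlation 0.5 to 0.7. Gradual loss (43.9%) is close to these; loss only by Day 28 (60.6%) is somewhat higher.

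The consequence is limited. The primary visit-specific effect sizes are untouched, and the trial is a pilot without a confirmatory test. The defect lies in the supportive test and in secondary outcomes and cortisol where the same four-visit model is used. It does not reach the CGI-I, which is not scored at baseline.

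**What to change.** In section 16.0:

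1. State that the outcome rows are Days 7, 14 and 28, that time is categorical, and that the Day 0 7-day BPDSI score is a covariate.
2. Assess change in the drug effect by the Day 28 minus Day 7 and Day 14 minus Day 7 differences in treatment effect, each with a 95% CI, alongside the planned visit-specific estimates. These contrasts replace the omnibus interaction as the answer to the question.
3. Apply the same structure to secondary outcomes and cortisol measured on the same four visits.
4. State that a non-significant interaction or contrast is not evidence that the effect was sustained.

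The cost is a few lines of SAP text and ESTIMATE statements in the planned SAS procedure, with no new data or visits. The small downside is that the intervals will be wide (half-width about 0.6 to 0.8 SD under the assumptions above), so the pilot will describe persistence, not establish it.

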17.0 Privacy/Confidentiality Issues

Confidentiality will be protected by ensuring all research staff have been properly trained in confidentiality and human subject research procedures, coding all subject information when possible, and by securing subject files in a locked filing cabinet or on secured databases with access available only to the principal investigator and research staff. Furthermore, data entered into a computer database will only use subject codes on secured computers that will be password protected with access available only to the principal investigator and research staff. Any screening information obtained from potential research subjects who subsequently do not participate in the research study will be destroyed.

21. Guy W. ECDEU assessment manual for psychopharmacology. Washington, DC: US Department of Health, Education, and Welfare;338:534-537. 1976.
22. Lobbestael, Arntz, Harkema-Schouten, & Bernstein (2009). Development and psychometric evaluation of a new assessment method for childhood maltreatment experiences: The Interview for Traumatic Events in Childhood (ITEC). *Child Abuse & Neglect*, 33, 505–1517.
24. Mifeprex [package insert]. Danco Laboratories, New York, NY, 2009..
25. Korlym [package insert]. Corcept Therapeutics Inc., Menlo Park, CA, 2000.

ATTACHMENT 1
Study Procedures Table

Visit	1	2	3	4	5	6
Day		0	4	7	14	28
Visit Window (days since last visit)		14-30	4	3	7	14
Informed Consent	X					
SCID I & II	X					
Medical History	X					
Demographics	X					
Physical Exam	X					
Vitals	X	X	X	X	X	X
Verification of Preg Prevention	X	X	X	X	X	X
ECG ^a	X	X	X	X	X ^b	X ^b
CGI-S/I	X ^c	X ^c		X	X	X
BPRS		X		X	X	X
BPDSI (90-day)	X					
BPDSI (7-day)		X		X	X	X
BPD Checklist		X		X	X	X
ITEC ^d	X					
SCL-90-R		X		X	X	X
IPII		X				X
CBC	X					
CMP	X	X		X	X	X
Serum Preg test (beta HCG)	X					
Blood Cortisol Level		X		X ^e	X ^e	X ^e
Biobank Blood Sample		X				X
Pharmacokinetics ^f				X		
Urine Pregnancy Test	X	X	X	X	X	X
Adverse Events			X	X	X	X
Concomitant Medication		X	X	X	X	X
Medication Dispensation		X				
Medication Accountability			X ^g	X		

a Triplicate tracings to be collected at least 1 minute apart

b Subsequent ECG tracings will be collected at V5 and V6 at the discretion of the principal investigator

c CGI-I will not be completed at Visits 1 or 2 as there is no "improvement" score at baseline.

d Clinician may use abbreviated version of form, at principal investigator's discretion

e Subsequent blood collection to occur at the exact time of day as the baseline value (+/- 30 minutes)

f Pharmacokinetic analysis will be completed based off of time of study drug from previous day.

g Study medication will be reviewed during this visit for compliance purposes. Study medication will not be returned or dispensed at this visit

NOTE: Visit split procedures will not be considered protocol deviations

V 02.03.15						
------------	--	--	--	--	--	--

ATTACHMENT 2
Concomitant Medication Table

Prohibited	
Class	Name/Subclass
Antibiotics	Anti-Malarials
	Anti-Mycoplasmics
	Azole Antifungals
	Chloramphenicol
	Fluoroquinolones
	Pentamidine
	Macrolides
Anesthetics/ Analgesics	Buprenorphine
	Fentanyl
	Methadone
	Sevoflurane
Anticonvulsant/ Mood-Stabilizers	Barbiturates
	Carbamazepine
	Oxcarbazepine
	Phenytoin
Antidepressants/ Anxiolytics/ Hypnotics	Benzodiazepines ^a (clonazepam is PERMITTED)
	Buspirone ^h (Caution. Uses of ≤ 30 mg total daily dose is PERMITTED)
	Bupropion
	Citalopram ^b (Caution. Uses of doses ≤ 20 mg daily dose is PERMITTED)--See additional notes
	Escitalopram ^c (Caution. Uses of doses ≤ 10 mg daily dose is PERMITTED)---See additional notes
	Eszopiclone ⁱ (Caution. Uses of ≤ 1 mg total daily dose is PERMITTED)
	Nefazodone
	Zaleplon ^j (Caution. Uses of ≤ 5 mg total daily dose is PERMITTED)
	Zolpidem ^l (Caution. Uses of ≤ 5 mg total daily dose is PERMITTED)
Antipsychotics/ Antiemetics	Aprepitant
	Asenapine
	Chlorpromazine
	Droperidol
	Haloperidol
	Iloperidone
	Ondansetron
	Paliperidone ^k
	Pimozide
	Quetiapine ^k
	Thioridazine
	Ziprasidone ^k

(continues on next page)

(continued from previous page)
 Concomitant Medication Table (Cont.)

Cardiovascular/ Dyslipidemics	Amiodarone
	Calcium Channel Blockers
	Clopidogrel
	Digoxin
	Disopyramide
	Dofetilide
	Dronedrone
	Flecainide
	Ibutilide
	Quinidine
	Sotalol
	Statins ^d
	Warfarin
Hematologies/ Oncologies	Anegrelide
	Arsenic Trioxide
	Chemotherapeutics
Herbals/Foods	Ginko Biloba
	Grapefruit
	Milk Thistle
	Star Fruit
	St. John's Wort
	Tonic Water
	Valerian
Others	Beta agonist (short acting) ^e
	Beta agonist (long acting)
	Corticosteroids ^{f,g}
	Conivaptan
	Cyclosporine
	Dihydroergotamine
	Efavirenz
	Ergotamine
	Mifepristone (Mifeprex, Korlym, RU486)
	Nevirapine
	Phosphodiesterase Inhibitors
	Pioglitazone
	Protease Inhibitors
	Replaglinide
	Sirolimus
	Tacrolimus
	Troglitazone

(continues on next page)

(continued from previous page)
 Concomitant Medication Table (Cont.)

a. Except for clonazepam, use of which is PERMITTED.
b. Caution. Uses of doses \leq 20mg daily dose is PERMITTED. Uses of doses $>$ 20mg daily dose, but $<$ 40mg daily dose is CAUTIONED due to the possibility of QTc prolongation. The subject may only be included in the study if QTc is within normal limits per a cardiologist overread of ECG tracings. Uses of doses $>$ 40mg daily dose is EXCLUSIONARY
c. Caution. Uses of doses \leq 10mg is PERMITTED. Uses of doses $>$ 10mg, but $<$ 20mg is CAUTIONED due to the possibility of QTc prolongation. The subject may only be included in the study if QTc is within normal limits per a cardiologist overread of ECG tracings. Uses of doses $>$ 20mg is EXCLUSIONARY.
d. Except for rosuvastatin, pitavastatin, & pravastatin.
e. Beta agonists (short acting) for PRN use are permitted. Subjects are to REFRAIN from use while on the study medication and for one week after discontinuation of study medication as using these medications as they may cause a temporary change in electrolyte levels which could increase the chance of a dangerous heart rhythm abnormality. If subjects require the use of these medications during this time period, they should be under the direct observation of a physician (e.g. on an inpatient unit, in an emergency room, or at a physician's office) for additional monitoring.
f. Topical and inhaled corticosteroids are OK.
g. Exclusionary: 4 weeks prior to randomization and on study medication
h. Caution. Uses of \leq 30mg total daily dose is PERMITTED. CAUTIONED due to the possibility of QTc prolongation. The subject may only be included in the study if QTc is within normal limits per a cardiologist overread of ECG tracings. Uses of doses $>$ 30mg daily dose is EXCLUSIONARY.
i. Caution. Uses of \leq 1mg total daily dose is PERMITTED. CAUTIONED due to the possibility of QTc prolongation. The subject may only be included in the study if QTc is within normal limits per a cardiologist overread of ECG tracings. Uses of doses $>$ 1mg daily dose is EXCLUSIONARY.
j. Caution. Uses of \leq 5mg total daily dose is PERMITTED. CAUTIONED due to the possibility of QTc prolongation. The subject may only be included in the study if QTc is within normal limits per a cardiologist overread of ECG tracings. Uses of doses $>$ 5mg daily dose is EXCLUSIONARY.
k. Caution. Due to the possibility of QTc prolongation. The subject may only be included in the study if QTc is $<$ 430msec cardiologist overread of ECG tracings and magnesium and potassium are within normal limits or determined not clinically significant by a principal investigator or medical designee.

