4. Clinically significant electrocardiogram (ECG) abnormality prior to randomization including: subjects with a corrected QT interval (Bazett's; QTcB) > 450 msec (male) or >470 msec (female) prior to randomization (based on the cardiologist overread). Repeat ECGs will be conducted at the discretion of the principal investigator or medical designee
5. Use of any exclusionary medication listed in Attachment 2: Concomitant Medication.
6. Pregnant or lactating women or women who plan to become pregnant or will be lactating within one month after cessation of study medication
7. Known IQ <70 based on medical history
8. Currently using an intrauterine device (IUD)
9. History of treatment with mifepristone or any mifepristone-containing medication at any time
10. Known history of (1) Hepatitis C virus antibody, (2) Hepatitis B surface antigen (HBsAg) with or without positive Hepatitis B core total antibody, or (3) HIV 1 or 2 antibodies
11. Subjects with moderate to severe renal impairment as defined by creatinine clearance (CrCl) < 60 ml/min (measured by the Cockcroft-Gault equation) at screening
12. Subjects with hepatic impairment as defined by liver transaminases or total bilirubin $> 3 \times$ upper limit of normal (ULN)
13. Subjects considered a high risk for suicidal acts, as determined by the principal investigator.
14. Subjects who have participated in a clinical trial with any pharmacological treatment intervention for which they received study-related medication in the 4 weeks prior to screening OR Subjects currently receiving treatment (within 1 dosing interval plus 4 weeks) with an investigational depot formulation of an antipsychotic medication
15. Subjects who demonstrate overtly aggressive behavior or who are deemed to pose a homicidal risk in the principal investigator's opinion
16. Psychosocial treatment changes 14 days prior to randomization
17. History of unexplained vaginal bleeding, endometrial hyperplasia with atypia, or endometrial carcinoma

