11.0 Criteria for Rescreening, Repeat Assessments, and Discontinuation

Repeat Assessments

Screening assessments can be repeated within the screening window under the same screening number with the exception of eligibility criteria related rating scales/questionnaires. Subject diagnosis confirmation will not be repeated.

Rescreening

Subjects who screen fail may be rescreened one time, under a new screening number. If a subject is rescreened, all screening assessments (with the exception of the diagnosis confirmation) must be repeated and the stability criteria timelines must be met.

Discontinuation

Subjects will be discontinued from the active treatment phase under the following circumstances:

1. Any psychosocial treatment changes
2. Suicide attempt
3. Missing 2 or more doses of study medication
4. Becoming pregnant
5. Developing a serious infectious disease
6. Have a change in stability criteria indicated in inclusion criteria #6
7. Subjects who require treatment with any excluded concomitant medications (See Attachment 2)

If subjects discontinue from the study, discontinuation assessments will be at the discretion of the

principal investigator.

A subject may withdraw from the study medication at any time at her own request, or may be withdrawn at any time at the discretion of the principal investigator for safety, behavioral, or administrative reasons.

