14.0 Adverse Events/Risks

For the purposes of collecting and evaluating all information found during this clinical study, an **adverse event** is any undesirable or unexpected experience that occurs after informed consent has been obtained without regard to the possibility of a causal relationship, and without regard to treatment group assignment. All adverse events will be documented and all serious adverse events will be reported following local Institutional Review Board (IRB) requirements.

For non-serious adverse events, research staff will question each subject and will document the occurrence and nature of presenting condition(s). Pre-existing condition(s) and any change in the pre-existing condition(s) will be documented and/or the occurrence and nature of any adverse event. Adverse events (AEs), especially those for which the relationship to study medication is not “unrelated,” will be followed up until they have returned to baseline status or stabilized at the discretion of the principal investigator. If after the follow-up period, return to baseline or stabilization cannot be established an explanation will be recorded in the source documentation.

The most common adverse events include:

- Nausea
- Vomiting

- Decreased appetite
- Diarrhea
- Fatigue
- Headache
- Dizziness
- Arthralgia
- Back pain
- High blood pressure

Females only:

- Endometrial hypertrophy
- Uterine cramping
- Vaginal bleeding

A **serious adverse event** is any adverse drug experience occurring at any dose that: results in death, is life threatening, results in inpatient hospitalization or prolongation of existing hospitalization, results in a persistent or significant disability/incapacity, or results in congenital anomaly/birth defect.

The following were considered serious adverse events in people with Cushing's syndrome and medical termination of pregnancy:

- Adrenal insufficiency
- Hypokalemia
- QT interval prolongation

It's not clear how frequently these serious adverse reactions may occur in an individual with BPD who does not have Cushing's syndrome and is not pregnant. This is because the vast majority of available safety data from clinical trials is for individuals with Cushing's syndrome or for women who used this medication for the termination of pregnancy and there is very little data available for people with neither condition.

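### QT prolongation and hypokalemia are named risks, but the plan counts only recorded adverse events, not new QTc or potassium exceedances by arm, and ECGs after Day 7 are optional

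*Combined protocol and SAP*

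**What the plan says.** Section 3.0 makes safety and tolerability Specific Aim 2. Section 14.0 lists QT prolongation and hypokalemia among the serious events seen in Cushing's syndrome and in medical termination of pregnancy. It adds that it is "not clear how frequently these serious adverse reactions may occur in an individual with BPD".

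Attachment 1 requires triplicate ECGs of everyone at Visits 1 to 4, the last three being Days 0, 4 and 7. It requires the CMP, which carries potassium, at screening and at Days 0, 7, 14 and 28. The ECG cells for Visits 5 and 6 (Days 14 and 28) carry footnote b: "Subsequent ECG tracings will be collected at V5 and V6 at the discretion of the principal investigator". No trigger is given. For those who leave, Section 11.0 says: "If subjects discontinue from the study, discontinuation assessments will be at the discretion of the" principal investigator.

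Section 16.0 has two sentences that bear on these data. One is general: "Continuous variables will be summarized by treatment groups using descriptive statistics including mean, standard deviation, and range". The other is the only named safety analysis: "Safety analyses of this study will include summarized counts and rates per treatment group of the incidence of the adverse events", with an exploratory Fisher test on selected events. Section 16.0 names no ECG or potassium outcome.

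The protocol does hold a QTc limit, but only for entry. Exclusion criterion 4 bars a QTcB "> 450 msec (male) or >470 msec (female) prior to randomization (based on the cardiologist overread".

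**The concern.** The trial collects an objective measurement for each of two named risks and then plans no analysis that uses it directly. A long QTc or a low potassium reaches the safety table only if the investigator decides that it is an adverse event. No on-study QTc or potassium value is defined as one, and the listed reasons for stopping treatment in Section 11.0 include no QTc criterion. Aim 2 would then rest on recording practice, although 24 subjects' readings are on file.

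The second part is smaller. After Day 7, whether an ECG exists depends on a decision about that subject. Discretionary repeats can protect the individual. They cannot support a count by arm, because the denominator is chosen. This also affects how ECG-based adverse events are found after Day 7, and what is known about subjects who leave early.

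**Working it through.** **1. The plan's own figure.** Section 16.0 gives 12 per group and Section 4.0 gives 24 randomized 1:1: 2 × 12 = 24, which agrees. The basis is a precision rule of thumb. No SD, event rate or dropout is given for QTc or potassium.

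**2. What is required after randomization (Attachment 1).**

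| | Day 0 | Day 4 | Day 7 | Day 14 | Day 28 |
|---|---|---|---|---|---|
| Triplicate ECG | required | required | required | optional | optional |
| CMP | required | none | required | required | required |

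- ECG sets at Days 4 and 7: 24 × 2 = 48, all required.
- ECG sets at Days 14 and 28: 24 × 2 = 48 subject-visits, 0 required.
- CMPs after Day 0: 24 × 3 = 72, all required, of which 48 fall at Days 14 and 28.

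The documents do not fix the day of the first dose, so the last dose is Day 6 or Day 7. The Day 7 ECG is therefore taken at the end of dosing or about one day later.

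**3. What the generic summary can show.** Mean, SD and range do not give the number of subjects beyond a limit. With the sex-specific entry limits, an arm maximum of 451 to 470 msec is above the limit for a man and within it for a woman, so the range alone cannot say whether even one subject exceeded it.

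**4. Why a chosen subset cannot be read by arm, even when blinded (illustration; all inputs assumed).** Let QTc change have SD 15 msec and the drug add 10 msec at Day 7. Suppose a Day 14 ECG is taken only if the Day 7 change exceeds 10 msec, with Day 7 to Day 14 correlation ρ of 0.3 to 0.7.

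- Placebo picked: P(Z > 10/15) = 0.25, or 3 of 12. Active picked: P(Z > 0) = 0.50, or 6 of 12.
- Mean standardized Day 7 value among those picked: 1.265 on placebo, 0.798 on active.
- Shift in the Day 14 arm difference = ρ × 15 × (0.798 − 1.265): about −2.1 msec at ρ = 0.3 and −4.9 msec at ρ = 0.7.

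Under this rule the subset understates a lasting drug effect by about 2 to 5 msec. A different picking rule would give a different figure.

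**5. Early leavers.** Each leaver without a closing ECG leaves 1/12 = 8% of an arm unknown from that point.

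**6. Chance findings if exceedances are counted.** If the local lower potassium limit is the 2.5th centile (assumed), 0.025 × 72 = 1.8 results fall below it by chance over the whole trial, and fewer once subjects low at Day 0 are excluded. For QTc, the highest of three independent normal readings is expected to lie 0.85 within-visit SD above their mean. The count should therefore use the mean of the triplicate. No QTc SD is given, so a chance QTc rate cannot be computed; the placebo arm would show it.

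**The case against.** The strongest reply is that no planned analysis is harmed. Section 16.0 names no QTc comparison at any visit, so a discretionary Day 14 ECG cannot bias one. That stands. A reader might infer that the plan contains an off-drug QTc comparison resting on a selected sample, but this would stretch one general sentence about continuous variables. The selection matters for any summary that might be made and for finding ECG-based adverse events.

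Existing protections also count. Day 4 and Day 7 ECGs are required of everyone. Vital signs, adverse events and the CMP continue to Day 28. The DSMB reviews adverse events at least quarterly, and QT-related co-medications are restricted. Section 14.0 follows adverse events until they return to baseline or stabilize. But that follow-up begins only once an event has been recorded, and no value triggers recording. Double-blinding stops selection on known arm, but not on Day 7 QTc or symptoms.

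Two further readings are tempting and should be resisted.

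- Attachment 2 footnote e tells subjects to "REFRAIN from use while on the study medication and for one week after discontinuation of study medication" because this "could increase the chance of a dangerous heart rhythm abnormality". A reader might take that week as a period of rhythm risk from mifepristone, ending at about Visit 5. The footnote concerns short-acting beta agonists and their effect on electrolytes. It says nothing about how long mifepristone affects QTc, and the required Day 14 CMP partly covers the mechanism it names.
- A reader might measure the gap by the upper bound on an event rate when none is seen among n tested, 1 − 0.05^(1/n): 22% for n = 12, rising to 78% for n = 2. Those bounds assume that the tested subjects are a random sample, which is exactly what discretion undermines. The documents set no n, and full testing would still leave 22%.

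**Conclusion.** The point holds as a minor improvement. The main gap is in Section 16.0: objective readings for two named risks are required of everyone, and Aim 2 makes no direct count of them. The second gap is that required ECGs stop at Day 7 (0 of 48 later subject-visits) and that leavers' assessments are optional, so off-drug QTc information comes from a chosen subset.

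The reach is limited. No stated analysis is biased, on-drug QTc is complete by design, and the BPDSI goal is unaffected. With 12 per arm the counts will be descriptive and cannot give a precise rate. The schedule and analysis facts come straight from the documents. The 2 to 5 msec distortion and the 1.8 chance potassium results rest on the assumptions stated with them, and the verdict does not depend on either.

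**What to change.** **Section 16.0 (main change).** Beside the adverse event table, report by arm, with the number tested:

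1. Subjects whose mean-of-triplicate QTcB on cardiologist overread is newly above 450 msec (male) or 470 msec (female).
2. Subjects whose potassium is newly below the local laboratory's lower limit.

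Newly means not present at Day 0. Whether a value is an adverse event stays with the investigator, and the choice of events for the Fisher test is left as it is.

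**Attachment 1 (cheap addition).** Require the Visit 5 triplicate ECG of all subjects. Keep Visit 6 discretionary unless the latest QTcB, defined as above, exceeds the limit; then require it.

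**Section 11.0 (cheap addition).** Ask any subject who leaves after the first dose for one triplicate ECG and one CMP.

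**Cost.** The counts use data already required. The Visit 5 change adds at most 24 ECG sets with overread at an existing visit, using a test already listed in that column. Visit 6 adds a few repeats, and each leaver who agrees adds one ECG and one blood draw. There is no new scheduled visit. Some low potassium values will be chance, and they should be read against the placebo arm.
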